10.8. Appendix 8: Values of Potential Clinical Importance

10.8.1. Laboratory Values

Note: Due to usage of local labs, care should be taken to ensure each supplied unit has been converted into the units given below before applying the PCI criteria (if applicable – any multipliers of LLN / ULN do not require units).

PCI values have been taken from Study ACE114622 (mild to moderate ARDS). Since no investigational product is being administered in this study any PCI flags will act more as an awareness for the study team when interpreting the RAS peptides / other clinical outcomes for those individuals. Any lab tests which the medical monitor has not specified PCI ranges for are denoted as “NA” but will still be reviewed as part of the Min/Max variables in the Summary tables.

Haematology				
Laboratory Parameter	Units	Category	Clinical Concern Range	
			Low Flag (Relative – Multipliers of LLN)	High Flag (Relative – Multipliers of ULN)
Platelet Count			0.4	NA
Red Blood Cell (RBC) Count			NA	NA
White Blood Cell (WBC) Count (absolute)			0.67	1.82
Haemoglobin		Male	0.67	1.03
		Female	0.67	1.13
Hematocrit	Ratio of 1	Male	0.3	0.54
		Female	0.3	0.54
(Total) Neutrophils			NA	NA
Lymphocytes			NA	NA
Monocytes			NA	NA
Eosinophils			NA	NA
Basophils			NA	NA

Clinical Chemistry				
Laboratory Parameter	Units	Category	Clinical Concern Range	
			Low Flag (Relative – Multipliers of LLN)	High Flag (Relative – Multipliers of ULN)
Urea / BUN			NA	NA
Chloride			NA	NA
Creatinine			NA	2
Potassium			0.86	1.10
Sodium			NA	NA
Total CO ₂			NA	NA
Total Bilirubin			NA	NA

Clinical Chemistry				
Laboratory Parameter	Units	Category	Clinical Concern Range	
			Low Flag	High Flag
Troponin I (Note: Has been spelt as Troponon in Protocol)	ng/mL		NA	> 0.04
Troponin T (Note: Has been spelt as Troponon in Protocol)	ng/mL		NA	> 0.10

10.8.2. Vital Signs

Vital Sign Parameter (Absolute)	Units	Clinical Concern Range	
		Lower	Upper
Systolic Blood Pressure	mmHg	<85	>160
Diastolic Blood Pressure	mmHg	<45	>100
Heart Rate	bpm	<40	>110

10.9. Appendix 9: Abbreviations & Trade Marks

10.9.1. Abbreviations

Abbreviation	Description
ADaM	Analysis Data Model
AE	Adverse Event
AIC	Akaike's Information Criteria
A&R	Analysis and Reporting
BLQ	Below Limit of Quantification
CDISC	Clinical Data Interchange Standards Consortium
CI	Confidence Interval
CPMS	Clinical Pharmacology Modelling & Simulation
CPSR	Clinical Pharmacology Study Report (interchangeable with the CSR abbreviation)
CS	Clinical Statistics
CSR	Clinical Study Report
CTR	Clinical Trial Register
CV _b / CV _w	Coefficient of Variation (Between) / Coefficient of Variation (Within)
DBF	Database Freeze
DBR	Database Release
DIC	Deviance Information Criteria
DOB	Date of Birth
DP	Decimal Places
eCRF	Electronic Case Record Form
EMA	European Medicines Agency
FDA	Food and Drug Administration
FDAAA	Food and Drug Administration Clinical Results Disclosure Requirements
GSK	GlaxoSmithKline
IA	Interim Analysis
ICH	International Conference on Harmonization
IDMC	Independent Data Monitoring Committee
IDSL	Integrated Data Standards Library
IMMS	International Modules Management System
IP	Investigational Product
ITT	Intent-To-Treat
LAR	Legally Acceptable Representative
LLN	Lower Limit of Normal
MMRM	Mixed Model Repeated Measures
PCI	Potential Clinical Importance
PD	Pharmacodynamic
PDMP	Protocol Deviation Management Plan
PK	Pharmacokinetic
PP	Per Protocol
PopPK	Population PK
QC	Quality Control

Abbreviation	Description
QTcF	Frederica's QT Interval Corrected for Heart Rate
QTcB	Bazett's QT Interval Corrected for Heart Rate
RAP	Reporting & Analysis Plan
RAMOS	Randomization & Medication Ordering System
SAC	Statistical Analysis Complete
SDSP	Study Data Standardization Plan
SDTM	Study Data Tabulation Model
SoA	Schedule of Assessments (also known as Time and Events table)
SOP	Standard Operation Procedure
TA	Therapeutic Area
TBC	To Be Confirmed
TFL	Tables, Figures & Listings
ULN	Upper Limit of Normal
ULQ	Upper Limit of Quantification

10.9.2. Trademarks

Trademarks of the GlaxoSmithKline Group of Companies	Trademarks not owned by the GlaxoSmithKline Group of Companies
NONE	SAS

10.10. Appendix 10: List of Data Displays

10.10.1. Data Display Numbering

The following numbering will be applied for RAP generated displays:

Section	Tables	Figures
Study Population	1.1 to 1.n	1.1 to 1.n
Safety	2.1 to 2.n	2.1 to 2.n
Pharmacodynamic and / or Biomarker	3.1 to 3.n	3.1 to 3.n
Participant Status and / or Other Clinical Assessments	4.1 to 4.n	4.1 to 4.n
Statistical Modelling	5.1 to 5.n	5.1 to 5.n
Section	Listings	
ICH Listings	1 to x	
Other Listings	y to z	

10.10.2. Mock Example Shell Referencing

Non IDSL specifications will be referenced as indicated and if required example mock-up displays provided in [Appendix 11: Example Mock Shells for Data Displays](#).

Section	Figure	Table	Listing
Study Population	POP_Fn	POP_Tn	POP_Ln
Safety	SAFE_Fn	SAFE_Tn	SAFE_Ln
Pharmacodynamic and / or Biomarker	PD_Fn	PD_Tn	PD_Ln
Participant Status and / or Other Clinical Assessments	OCA_Fn	OCA_Tn	OCA_Ln
Statistical Modelling	SM_Fn	SM_Tn	SM_Ln

NOTES:

- Non-Standard displays are indicated in the 'IDSL / Example Shell' or 'Programming Notes' column as '[Non-Standard] + Reference.'

10.10.3. Deliverables

Delivery Priority ¹	Description
SAC X	Final Statistical Analysis Complete

NOTES:

- Indicates priority (i.e. order) in which displays will be generated for the reporting effort

10.10.4. Study Population Tables

Study Population Tables					
No.	Population	IDSL / Example Shell	Title	Programming Notes	Deliverable [Priority]
Subject Disposition					
1.1.	Enrolled	ES1	Summary of Subject Disposition for the Subject Conclusion Record	ICH E3, FDAAA, EudraCT, CONSORT	SAC 1
1.2.	Screened	ES6	Summary of Screening Status and Reasons for Screen Failure	Journal Requirements	SAC 1
1.3.	Safety	NS1	Summary of Number of Subjects by Country and Site ID	EudraCT/Clinical Operations	SAC 1
Protocol Deviations					
1.4.	Safety	DV1	Summary of Important Protocol Deviations	ICH E3	SAC 1
Population Analysed					
1.5.	Enrolled	SP1A	Summary of Study Populations	IDSL	SAC 1
1.6.	Enrolled	SP2A	Summary of Exclusions from the Safety/Evaluable/Completed/At Risk Populations	IDSL If possible separate page for each population (this may require non-standard wrapper macro to call the standard macro separately for each population) If the Evaluable with prohibited conmed population is different to evaluable add it in (otherwise footnote the evaluable table to indicate they are the same)	SAC 1

Study Population Tables					
No.	Population	IDSL / Example Shell	Title	Programming Notes	Deliverable [Priority]
Demographic and Baseline Characteristics					
1.7.	Safety	DM1	Summary of Demographic Characteristics by PCD/ACP status	
ICH E3, FDAAA, EudraCT
 
Instead of the set of treatment variables (columns) please use "No PCD/ACP" and "Any PCD/ACP" and "All Participants" as columns to group the subjects
 
As well as the standard set of demography items (Sex, Age, Age Group, Height, Weight, BMI) please also include the following Disease specific baseline variables (with units if applicable) to facilitate manuscript publication (mixture of continuous and categorical variables)
 
Baseline should be the earliest non-missing value from SCREENING or DAY 1 visits. Do not display values from Days 2 or 3 (if multiple timepoints are available for an item)
 
SAPSII, SOFA, PaO2/FiO2 (from SOFA form), PaO2, FiO2, PaCO2, Oxygenation Index, Reason for Intubation (use the mapped variable not free text results), Proned, Receiving Inhaled Nitric Oxide, "Managed with Vasopressors, inotropes or other vasoactive agents", ECMO, ECCO2R, Global Inhomogeneity Index, SpO2, Serum Lactate, Serum Bicarbonate, pH, Base excess (arterial whole blood), Base deficit (arterial whole blood), Central Venous Pressure, Static respiratory system compliance, Respiratory rate (not from vitals but from FAPR), Pressure support (Y/N), Tidal Volume, PEEP, Peak Pressure, Plateau Pressure, Mean Airway Pressure, Driving Pressure, In-hospital Mortality (Y/N/Unknown)
 
Note: Summarise with n, Median, Lower and Upper quartiles, Min and Max:
 
Length of stay in ICU, Length of stay in hospital, Ventilation free days
	SAC 2

Study Population Tables					
No.	Population	IDSL / Example Shell	Title	Programming Notes	Deliverable [Priority]
1.8.	Safety	DM11	Summary of Age Ranges	EudraCT	SAC 2
Prior and Concomitant Medications					
1.9.	Safety	MH4	Summary of Current Medical Conditions	ICH E3	SAC 2
1.10.	Safety	MH4	Summary of Past Medical Conditions	ICH E3	SAC 2
1.11.	Safety	CM1	Summary of Concomitant Medications	ICH E3 Exclude the SOFA related records	SAC 2

10.10.5. Safety Tables

Safety: Tables					
No.	Population	IDSL / Example Shell	Title	Programming Notes	Deliverable [Priority]
Serious Adverse Events					
2.1.	Safety	AE16	Summary of Serious Adverse Events by System Organ Class and Preferred Term (Number of Participants and Occurrences)	FDAAA, EudraCT Conditional output: a listing on its own may be sufficient if there are few events. Display lines showing "Drug-related SAE" and "Drug-related Fatal SAE" should be omitted as there is no study drug involved.	SAC 2
Laboratory					
2.2.	Safety	LB1	Summary of Clinical Chemistry Values by Timepoint	ICH E3 Exclude the SOFA related records There is no baseline in this study as there is no treatment being administered. Therefore the only data that can be presented is raw values rather than changes from baseline.	SAC 2

Safety: Tables					
No.	Population	IDSL / Example Shell	Title	Programming Notes	Deliverable [Priority]
2.3.	Safety	LB1	Summary of Haematology Values by Timepoint	ICH E3 Exclude the SOFA related records There is no baseline in this study as there is no treatment being administered. Therefore the only data that can be presented is raw values rather than changes from baseline.	SAC 2
Vital Signs					
2.4.	Safety	VS1	Summary of Vital Signs by Timepoint	ICH E3 Exclude the SOFA related records There is no baseline in this study as there is no treatment being administered. Therefore the only data that can be presented is raw values rather than changes from baseline.	SAC 2

10.10.6. Pharmacodynamic and Biomarker Tables

Pharmacodynamic and Biomarker: Tables					
No.	Population	IDSL / Example Shell	Title	Programming Notes	Deliverable [Priority]
Echocardiography					
3.1.	Evaluable	PD_T1 (ECHO)	Summary of Echocardiogram Measurements by Timepoint	Two separate statistics tables: 1) for continuous, 2) for qualitative echo measurements.	SAC 1
3.2.	Evaluable	SM_T1 (ECHO)	Within- and Between-Subject Variability of Continuous Echocardiogram Measurements		SAC 1
RAS Biomarkers					
3.3.	Evaluable	PD_T2 (RAS)	Summary of RAS Biomarker Measurements by Timepoint	Present results for levels and log transformed in two separate tables.	SAC 1
3.4.	Evaluable	SM_T1 (RAS)	Within- and Between-Subject Variability of RAS Biomarker Measurements		SAC 1

Participant Status and Other Clinical Assessments: Tables					
No.	Population	IDSL / Example Shell	Title	Programming Notes	Deliverable [Priority]
Disease Diagnosis Status					
4.1.	At risk	OCA_T1 (DISEASE_INCIDENCE)	Summary of ARDS, PCD and ACP Incidence Rates by Timepoint and Study	Create two tables: 1) summarizing of number of the cases, where patient may contribute multiple times and 2) with overall incidence rates including the joint categories. Note: Shell does not contain all items to be displayed	SAC 1

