Attenuation of RAS-mediated vasoconstriction, without compromising the normo-adaptive pulmonary vascular response, may improve pulmonary blood flow, cardiac output, ventilation/perfusion matching and reduce afterload which should ultimately improve outcomes in mechanically ventilated patients. RAS mediated vasoconstriction might be improved through the dual action of angiotensin converting enzyme (ACE2) by simultaneously reducing Ang II and forming Ang(1-7). Thus, increasing the total amount of active enzyme may be beneficial in the treatment of RV dysfunction in patients with severe respiratory failure [Tom 2001; Idell 1987; Santos 2003; Wenz 2000].

Data exploring the RAS status and its association with acute changes in pulmonary hemodynamics and worsening RV function is limited in patients with severe respiratory failure, including in those who are mechanically ventilated. This study is designed to test the hypothesis that an association exists between RAS peptides, primarily plasma Ang II and Ang(1-7) levels, and RV function in mechanically ventilated patients. The hypothesis will be tested by assessing the plasma levels of RAS peptides and RV function as measured by echocardiography assessing RV size, septal kinetics and degree of pulmonary hypertension as measured by pulmonary arterial systolic pressure (PASP). A secondary aim of the study is to further characterise this population to inform future interventional studies, by assessing the incidence and severity of RV dysfunction, and assessing the variability of key echocardiographic parameters including RV size and PASP as well as RAS peptide levels in mechanically ventilated patients. An exploratory aim of the study is to consider regional lung ventilation and perfusion assessed by global inhomogeneity index, which may improve understanding of ventilation/perfusion matching in patients undergoing mechanical ventilation with changes in pulmonary vascular resistance.

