10.3. Statistical Analyses

10.3.1. Pharmacodynamic Analyses

Endpoint	Statistical Analysis Methods
Primary	
The association of Ang II with RV function (measured by PASP and RV size ratio) will be modelled using a Bayesian repeated measures mixed effects linear regression model, where PASP and RV size ratio are joint response variables, and including subject as a random effect and log(Ang II), age and sex as fixed effects. The model will be used to make a probabilistic prediction of PASP and RV size ratio for two reference values of Ang II, and hence an estimate for the probability of RV dysfunction (defined as PASP > 40 mmHg or RV size ratio > 0.6, following Boissier 2013) for the two given Ang II levels will be obtained using mean values for the other continuous covariates and averaging over all levels of class effects for categorical covariates.
 
The above modelling may use a modified Ang II value (modification based on the corresponding Ang(1-7) result to account for potential inhibitory interactions); details to be provided in the reporting and analysis plan (RAP).
 
The primary analysis will use the Evaluable population.

Secondary	
Association of Ang(1-7) with RV function (measured by PASP and RV size ratio) and of Ang II/Ang(1-7) with RV function (measured by PASP and RV size ratio) will both be modelled as per the primary analysis described above. These analyses will be done using the Evaluable population.
 
A model including both Ang II and Ang(1-7) as co-predictors of RV function may also be built, to explore the relationship between RV function and the envisaged dual action of angiotensin converting enzyme (ACE)2 effecting a reduction in Ang II together with a simultaneous increase in Ang(1-7).
 
Incidence of PCD and ACP during the three days of the study period and prevalence of pre-existing PCD/ ACP on entry to the study will be reported with 95% confidence intervals. This analysis will be done using the Completed population (which includes a clause to include participants who have an onset of PCD/ ACP but are subsequently withdrawn from the study before all three days' worth of data are collected without withdrawing consent).
 
The distribution of PASP, RV size ratio and other measurements of RV function in mechanically ventilated participants will be assessed via a combination of descriptive summary tables and outputs from the statistical modelling.

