4. ANALYSIS POPULATIONS

Population ¹	Definition / Criteria	Analyses Evaluated
Screened	All participants who have been screened.	
• To aid construction of Consort diagram in any publication
Enrolled	All participants who had passed screening and who had appropriate informed consent (via any of the processes described in the protocol).	
• Summary of Subject Status and Reason for Study Withdrawal• Summary of Study Populations• Summary of Exclusions from the

Population ¹	Definition / Criteria	Analyses Evaluated
		Safety/Completed/ Evaluable Populations
Safety	All participants for whom at least one echocardiograph and/or blood sample has been taken, and who did not retrospectively withdraw the consent.	
 • Study population (excl. specific tables mentioned below) • Safety
Evaluable	All participants for whom PASP, RV size ratio, Ang II and Ang(1-7) data have been recorded for at least one study time point, and who did not retrospectively withdraw the consent (and who still had at least one study time point of data remaining after accounting for any prohibited concomitant medications (for example but not limited to renin inhibitors, ARBs or ACE inhibitors) – See Section 10.1.1).	
 • Pharmacodynamic/ Biomarker (excl. disease diagnosis status)
Evaluable with Prohibited Con Meds	All participants in the Evaluable population plus any participants who were excluded from the Evaluable population because of prohibited concomitant medications (for example but not limited to renin inhibitors, ARBs or ACE inhibitors)	
 • Sensitivity for Primary analysis (conditional on number of prohibited con meds)
Completed ²	All participants for whom PASP, RV size ratio, Ang II, and Ang(1-7) data have been recorded for all three study days.	
 • Disease diagnosis status
At Risk	
For the purpose of evaluating ACP/PCD and ARDS incidence rates the participants who satisfy
 
1) PASP and RV size ratio recorded for all three study days (regardless of the Ang II and Ang(1-7) status)
 
and/or
 
2) databased ACP/PCD and/or ARDS assessment during the study period (even if they do not have three days' worth of study assessments for the above echo outcomes)
 
provided consent is not withdrawn.
	
 • Disease diagnosis status

NOTES :

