1. Please refer to Section 10.10: List of Data Displays which details the population to be used for each display being generated.
2. Modifications to the Completed population listed in study protocol to assist with production of summary and incidence rate calculations for ACP/PCD status (include creating a new population "At Risk" to be used with selected incidence rate displays that is independent of the RAS biomarker availability). The remaining completed population is not formally used, but will provide feasibility information (i.e. could we measure items reliably in the "real world" of the ICU)

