7.2.3. Population of Interest

The secondary pharmacodynamic analyses will be based on the Evaluable population, unless otherwise specified.

All analyses involving incidence rate endpoints will be based on the At Risk population unless otherwise specified.

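### The echocardiogram summary and variability displays use the Evaluable population, so participants with usable echoes but no time point carrying PASP, RV size ratio and both peptides are left out

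*SAP*

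**What the plan says.** **The descriptive aim.** Protocol 3.2 names a secondary aim of characterising this population to inform later interventional studies, in part by "assessing the variability of key echocardiographic parameters including RV size and PASP as well as RAS peptide levels in mechanically ventilated patients". Protocol 10.3.1 lists under the secondary analyses: "The distribution of PASP, RV size ratio and other measurements of RV function in mechanically ventilated participants will be assessed". It adds that this will be done through descriptive tables together with model output. It names no population for this summary.

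**The population chosen.** In SAP 10.10.6, Table 3.1 ("Summary of Echocardiogram Measurements by Timepoint") and Table 3.2 ("Within- and Between-Subject Variability of Continuous Echocardiogram Measurements") are both labelled Evaluable. So are Figure 3.1 (PASP against RV size ratio, SAP 10.10.7) and Listing 13 (SAP 10.10.11). This follows the default in SAP 7.2.3: "The secondary pharmacodynamic analyses will be based on the Evaluable population, unless otherwise specified".

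**What Evaluable requires.** SAP section 4 defines it as "All participants for whom PASP, RV size ratio, Ang II and Ang(1-7) data have been recorded for at least one study time point", subject to consent, and limits it to those "who still had at least one study time point of data remaining after accounting for any prohibited concomitant medications".

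**What was done for incidence.** Note 2 to SAP section 4 explains that At Risk was created for selected incidence displays so that they would be "independent of the RAS biomarker availability". The echo tables were not given an equivalent. No echo summary on any wider population is planned.

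**The concern.** An echocardiogram can be described without a peptide assay, and RV size ratio, TAPSE or LV ejection fraction can be described without a PASP. Tying the echo tables to Evaluable makes the description conditional on assay success and on a derivable PASP. The result describes ventilated patients who happened to have a complete set, not ventilated patients in general. The SAP recognised the peptide dependence for incidence and removed it there, but not here.

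The tables are meant to help plan later studies, so the means and standard deviations they supply matter. Two things are at stake. Precision is given up without need in a study that stopped early. There may also be selection, if participants without a complete set differ in RV size or pressure from those with one.

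**Working it through.** **1. Which rows are affected.** The four-value requirement is read, as the primary model needs it, as all four values at one time point.

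| Why no time point is complete | PASP rows | RV size ratio and other echo rows | Figure 3.1 |
|---|---|---|---|
| No usable Ang II or Ang(1-7) on any day | lost, recoverable | lost, recoverable | lost, recoverable |
| PASP never derivable | no value under any population | lost, recoverable | cannot be plotted |

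The second route is foreseeable. Table 7 in SAP 10.6.6 sets PASP to missing whenever the tricuspid gradient or the right atrial pressure is missing. Protocol 9.5.3 anticipates an unmeasurable gradient and gives an acceleration-time substitute for the diagnosis, but Table 7 has no substitute value for PASP.

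**2. The plan's own precision figure.** The only one for the secondary objectives is ±5 percentage points for ACP incidence at N = 150 and 10% (protocol 10.1). Check: 1.96 × √(0.10 × 0.90 / 150) = 0.0480, or 4.80 points, which rounds to 5. It reproduces, and this point does not alter it. No precision figure is given for the echo tables.

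**3. How many could be lost.** The documents do not say. Suppose a fraction q of visits lack a complete set, with three visits each. The share of participants excluded is q³ if days are independent and q if the same participants are affected every day. For q = 0.20 that is 0.8% to 20%; for q = 0.50, 12.5% to 50%. The value of q is an assumption.

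**4. Precision.** If a fraction f is excluded, an interval for a mean widens by 1/√(1 − f): 1.05 at f = 0.10, 1.12 at 0.20 and 1.20 at 0.30. The half-widths below are 1.96 × SD/√n, with the planning SDs of protocol 12.5.4 (8 mmHg and 0.15) and one value per participant. N = 50 is an assumed size after early termination.

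| Participants with an echo | f | n | PASP (mmHg) | RV size ratio |
|---|---|---|---|---|
| 150 | 0 | 150 | 1.28 | 0.024 |
| 150 | 0.10 | 135 | 1.35 | 0.025 |
| 150 | 0.30 | 105 | 1.53 | 0.029 |
| 50 | 0 | 50 | 2.22 | 0.042 |
| 50 | 0.10 | 45 | 2.34 | 0.044 |
| 50 | 0.30 | 35 | 2.65 | 0.050 |

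The PASP column applies only to participants excluded for reasons other than a missing PASP.

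**5. Selection.** The shift in a displayed mean is f × (mean of included − mean of excluded). If the two groups differ by 0.5 SD, RV size ratio shifts by 0.10 × 0.075 = 0.0075 at f = 0.10 and by 0.30 × 0.075 = 0.0225 at f = 0.30. With the same restriction as above, PASP shifts by 0.10 × 4 = 0.4 mmHg and 0.30 × 4 = 1.2 mmHg.

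A worked example for the PASP route, all of it assumed: 20% never have a derivable PASP, and their true PASP is 8 mmHg lower. Carried through the planning correlation of 0.5, their RV size ratio is 0.5 × 0.15 = 0.075 lower. With an overall mean of 0.61, the included mean is 0.61 + 0.20 × 0.075 = 0.625. Keeping the SD at 0.15, P(ratio > 0.6) is 1 − Φ((0.6 − 0.625)/0.15) = 0.566, against 1 − Φ((0.6 − 0.61)/0.15) = 0.527. The shift of 0.015 is 0.1 SD, smaller than the half-width of 0.024 at N = 150.

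**The case against.** The strongest reply is that Evaluable is the SAP's consistent default for pharmacodynamic displays. The formal echo-based secondary objective, PCD and ACP incidence, already has its own population. The distribution summary is not a row in the objectives table. Protocol 10.3.1 draws it partly from the models, which properly use Evaluable. One complete time point keeps a participant in, and SAP 10.1.1 removes only the affected days when one or two fail. Exclusions by population are tabulated and listed (Table 1.6, Listing 5), and the covariate dataset in SAP 10.6.10 keeps visits with either PASP or RV size ratio, so nothing vanishes from the data. The size of any loss or bias is assumed throughout.

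All of this stands as a limit on the point. It does not explain why an RV size ratio should need a peptide result before it is summarised. Showing how many were excluded does not show what their echoes looked like.

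A simple switch to Safety would also be wrong. Safety admits participants with only a blood sample, and it lacks the echo-quality rule in SAP 10.1.1 item 02. The fix has to supply both conditions.

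**Conclusion.** The point holds as a weakness in the SAP's choice of population for descriptive displays. A participant with usable echoes but no complete time point is left out of Tables 3.1 and 3.2, Figure 3.1 and Listing 13 without a reason that the description itself requires. The primary model and the incidence estimates are untouched. On an assumed 10% to 30% excluded, intervals are about 5% to 20% wider than needed. The direction and size of any bias are unknown.

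A reader might infer more, and the documents do not support it:

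- **A breach of the protocol.** The protocol names no population for this summary, and the aim in 3.2 covers peptide variability as well as echo measures.
- **Loss after any missing sample.** Exclusion requires that no time point be complete. The SAP does not say whether a good echo on a day without peptide data stays in Tables 3.1 and 3.2; that should be settled.
- **Wholesale removal for prohibited medication.** SAP 10.1.1 item 03 removes post-medication observations, subject to the medical monitor's opinion. The participant goes only if nothing remains.
- **Known assay losses.** SAP 3.1 reports that technical issues with the assay delayed the first interim analysis, not that samples failed.
- **A cure for selection in PASP.** PASP rows and Figure 3.1 remain limited to participants with a derivable PASP whatever population is used.

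**What to change.** Run Tables 3.1 and 3.2, Figure 3.1 and Listing 13 on Safety participants with at least one evaluable echocardiogram, keeping the echo-quality exclusion of SAP 10.1.1 item 02. State that every evaluable echo time point is used whether or not peptide data exist for that day, and show n for each measure. Add a note that PASP rows describe only participants with a derivable PASP. Keep Evaluable for the association models and, if wanted, as a supporting version of the tables.

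The cost is a change to the population column, a short programming rule and a rerun. The descriptive N will differ from the model N, and a footnote can explain this; the SAP already uses different populations for Table 1.7 (Safety) and Table 4.1 (At Risk). A parallel change to the peptide displays (Tables 3.3 and 3.4, Listing 14) is optional and does not follow from this argument.
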